16.1.2 Sample Size

This study will enroll a total of 30-36 patients, of which 20-24 will be assigned to the intervention and 10-12 assigned to control. The objective of this study is to pilot test the newly adapted STC intervention for women with gynecologic cancer and to allow us to calculate effect sizes, if appropriate, that will inform a larger R01 trial that is expected to follow from this study. We selected 30 participants to participate in this trial because it is a large enough sample to provide ample pilot data while maintaining adequate feasibility in the time allotted. The target sample size is similar to those used in successful prior pilot trials used by the study team.¹⁰⁹ Further, we have chosen a 2:1 allocation to the STC condition, which allows us to gather greater information from participants in this condition, our primary interest, relative to the control condition. The operating characteristics of the feasibility and acceptability rules for this pilot study are given in Table 4. Although we may over-recruit to ensure adequate communication data, feasibility and acceptability rules (see Table 4) will be conducted using the first 30 participants. Probabilities were calculated using the negative binomial distribution for enrollment, and using the binomial distribution for all other feasibility and acceptability benchmarks.

Table 4: Operating characteristics of feasibility and acceptability decision rules

Criteria	Decision rule	Favorable condition	Unfavorable condition	Probability of declaring success if favorable	Probability of declaring success if unfavorable
Enrollment	≥ 60% enrolled (30 accrued with ≤50 approached)	75%	45%	99%	2%
Retention	≥ 80% enrolled (≥ 24/30 enrolled)	90%	65%	97%	6%
Completion	≥70% complete (≥14/20 on STC arm)	80%	50%	91%	6%
Acceptability	≥75% endorse at least 6/8 items (≥15/20 on STC arm)	85%	55%	93%	6%

17.0 Data Safety Monitoring Plan

The PI will take responsibility for monitoring the safety of all phases of the research study. The research assistant or other study team member will report any adverse events he or she observes to [name] immediately. The study consent forms have the contact information for the study PI and the Institutional Review Board (IRB), and patients may contact her or the IRB at any time. The research team will keep a log tracking the number, nature, and frequency of adverse events that occur in both recruiting sites and overall. Because of the nature of the research as involving procedures without significant risk (e.g., surveys; online video intervention) there are unlikely to be any related adverse events. Given the minimal risk of this study, it is determined that a Data and Safety Monitoring Board is not necessary for the proposed study.

18.0 Adverse Events

Because of the nature of the research as involving procedures without significant risk (e.g., surveys; brief communication skills training program) there are unlikely to be any serious adverse events and adverse events are likely to be rare. Possible risks include feeling worried, anxious, or concerned during questionnaire completion or during the intervention. All participants are informed of possible adverse psychological reactions associated with participating in the study during the informed consent process.

Any unexpected or adverse event that occurs during data collection or study procedures is reported immediately to the Principal Investigator, who is responsible for documenting all adverse events with the FCCC IRB within 24 hours. For participants who are experiencing psychological distress reactions, the study team member or research assistant alerts the Principal Investigator, who would provide the participant with a referral to appropriate services. At FCCC counselors in the Department of Social Work are trained to provide psychological support services or to make specific referrals to other psychological counseling or psychiatric services in the area as needed.

The research team will keep a log tracking the number, nature, and frequency of adverse events as part of each phase of the research plan. In accordance with FCCC guidelines, this protocol will employ the following mechanisms for adverse event reporting: 1) alert the FCCC review committees of any and all reports of adverse events; 2) inform all members of the study team of any all reports of adverse events. If 3 or more adverse events are reported, the study team will assess potential causes of the adverse events and, if events are clearly linked to study participation, discontinue the study.

19.0 Quality Assurance Procedures and Participant Confidentiality

We have designed standardized procedures for every aspect of study administration, from the candidate screening process to administration of the study conditions. Second, all outcome measures have demonstrated excellent psychometric properties and have prior research supporting their appropriateness in the study population and sensitivity to interventions. Third, REDCap, a secure web-based application, will be used for data collection and for randomization, with an automated procedure that limits prediction of allocation and protects masking of allocations. Paper versions of surveys (e.g., post-intervention surveys collected in clinic) will be entered into REDCap by study staff, and the paper versions of the surveys will be locked in a file cabinet containing no identifying information (e.g., surveys are labeled with a random study ID). Only study staff will have access to the REDCap database and the paper versions of the surveys. All files related to study participation (e.g., tracking files) will be kept on [name] drive on the Fox Chase network and will be password protected. Finally, to facilitate unbiased data collection and analysis the following steps are taken: 1) the data analyst will conduct outcome data analyses on data in which study condition is masked; 2) outcome data collection is completed in an automated fashion using REDCap, minimizing the need for contact with participants to collect study data. On an annual basis, adverse events will be reviewed across study conditions. During the annual review of adverse events, the presence of significant between-group differences could potentially warrant unmasking of the study conditions by the study biostatistician.

Information about study subjects will be kept confidential and managed according to the requirements of the Health Insurance Portability and Accountability Act of 1996 (HIPAA). Those regulations required a signed subject authorization informing the subject of the following: The protected health information (PHI) that will be collected from patient; who will have access to that information and why; who will use or disclose that information; the rights of a research subject to revoke their authorization or use their PHI. In the event that a participant revokes authorization to collect or use PHI, the investigator, by regulation, retains the ability to use all information prior to the revocation of subject authorization. To ensure confidentiality identifiers will be recorded and used with electronic data collected and all records will be secured in a locked location.

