7.0 Randomization

Randomization will occur once the patient has consented and completed the baseline (T1) survey. Using a similar approach as was used successfully in our prior breast cancer trial, patients will be randomized with an allocation ratio of 2:1 to either the STC intervention (video, workbook, and resource guide) or control condition (resource guide only). The statistician ([name]) will generate the randomization sequences using an automated randomization procedure in REDCap that limits prediction of allocation and protects masking of allocations. The automated randomization function in REDCap will inform the Research Lab Manager of the patient's assigned treatment condition. Randomization in blocks of six will guarantee that, after every six assignments, the study arms will have equal numbers.

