16.1.1. Primary and Secondary Outcome Variables

16.1.1.1. Primary outcomes are feasibility and acceptability of the study. Feasibility will be measured through study enrollment, retention (defined as completion of the final survey), and intervention completion (defined as engaging in some or all of the intervention components (i.e., video and workbook; STC arm only)). We will also assess completion of the resource guide across both study conditions, although these data will not be used to determine feasibility. Acceptability is measured using standard self-report items obtained at post-intervention (immediately following clinic encounter); specifically, these items assess intervention satisfaction, informativeness, helpfulness, relevance, ease of participation, liking the format, likelihood of recommending to others, and perceived importance of the program for people with gynecologic cancer.

16.1.2.1. Feasibility. The proportion of study subjects meeting each feasibility measure will be calculated. The following rates will be used as benchmarks for feasibility: Enrollment \geq 60% of eligible candidates; retention \geq 80%; and intervention completion \geq 70%. For enrollment, we will approach patients until clinical communication data are collected on 30 participants, and then stop approaching patients. If we meet our target of 30 enrollments by approaching 50 or fewer patients, the intervention will be declared as feasible.

16.1.2.2. Acceptability. At the individual level, we will determine whether the individual met our acceptability criteria, which we define as endorsing 75% of the 8 acceptability items for the core components of the STC intervention (video and workbook; at least 6 out of 8 items). If 75% of the STC sample (n=15) meets that definition, then we will be able to say that overall the study meets the standard set for acceptability. Other data obtained from the acceptability surveys (e.g., length of time spent using intervention materials, qualitative survey responses) will be analyzed descriptively or using thematic analysis as appropriate. These items will be analyzed across both conditions.

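### The analyst masking stated in Section 19.0 cannot survive any by-arm summary under 2:1 allocation, or the STC-only rules; limit the statement to the steps it can cover

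*Combined protocol and SAP*

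**What the plan says.** Section 19.0 introduces two measures with the words "to facilitate unbiased data collection and analysis the following steps are taken". The first is that "the data analyst will conduct outcome data analyses on data in which study condition is masked"; the second is automated data collection in REDCap. The same section allows the study biostatistician to unmask if adverse events differ between groups, so the plan treats masking as being in force. It does not say how masking is done, which analyses it covers, or whether the data analyst is the statistician who generates the randomization sequences in Section 7.0.

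On allocation, Section 7.0 says "patients will be randomized with an allocation ratio of 2:1 to either the STC intervention", and Section 16.1.2 (Sample Size) gives the resulting arms: "This study will enroll a total of 30-36 patients, of which 20-24 will be assigned to the intervention and 10-12 assigned to control". Section 7.0 also says "Randomization in blocks of six will guarantee that, after every six assignments, the study arms will have equal numbers".

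Section 16.1.1.1 makes feasibility and acceptability the primary outcomes. Intervention completion is limited to one arm ("i.e., video and workbook; STC arm only"). Section 16.1.2.2 judges acceptability on the STC sample, from eight items about the video and workbook. Under Section 8.2 controls receive neither. Section 16.1.2.3 makes the preliminary efficacy analysis descriptive, without hypothesis tests.

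**The concern.** Replacing arm names with codes hides the arm only if nothing else in the file gives it away. Here two things do: the unequal group sizes, and outcomes that exist or are judged in one arm only. Either one shows the analyst which women had the intervention.

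Some choices are still open for masking to protect. Section 16.1.2.2 gives no response cut-off for endorsing an acceptability item. Section 16.1.2.3 gives no cut for the strata of sexual concerns and does not define the standard effect size, and Sections 4.1 and 16.1.2 make effect sizes conditional on being appropriate. If these are settled after the arms are recognisable, a report that repeats Section 19.0 would describe a protection that was not in place for those decisions.

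**Working it through.** **1. The plan's own figures reproduce.** Table 4 uses 30 women for retention and 20 STC women for completion and acceptability. With Bin(n, p) for a binomial count:

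- Enrollment, P(Bin(50, p) ≥ 30): 99.4% at p = 0.75 and 2.4% at p = 0.45 (plan: 99%, 2%).
- Retention, P(Bin(30, p) ≥ 24): 97.4% at 0.90 and 5.9% at 0.65 (plan: 97%, 6%).
- Completion, P(Bin(20, p) ≥ 14): 91.3% at 0.80 and 5.8% at 0.50 (plan: 91%, 6%).
- Acceptability, P(Bin(20, p) ≥ 15): 93.3% at 0.85 and 5.5% at 0.55 (plan: 93%, 6%).

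Table 4 is sound, and its denominators confirm 20 STC women among the first 30.

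**2. Arm sizes.** A block of six at 2:1 holds 4 STC and 2 control. Five blocks give 5 × 4 = 20 v 5 × 2 = 10; six blocks give 24 v 12. For N between 30 and 36, with r = N − 30 women in the sixth block, STC lies between 20 + max(0, r − 2) and 20 + min(4, r), and control is N minus STC:

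| N | STC | Control |
|---|---|---|
| 30 | 20 | 10 |
| 31 | 20–21 | 10–11 |
| 32 | 20–22 | 10–12 |
| 33 | 21–23 | 10–12 |
| 34 | 22–24 | 10–12 |
| 35 | 23–24 | 11–12 |
| 36 | 24 | 12 |

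The smallest STC arm (20) exceeds the largest control arm (12), so as randomised the larger coded group is STC with certainty.

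**3. After dropout.** Let X ~ Bin(20, p) and Y ~ Bin(10, p) be the women analysed in each arm. The quantity is P(X > Y), the sum of P(X = i) P(Y = j) over i > j. The values of p are the Table 4 retention conditions (65%, 90%) and the 80% benchmark.

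| Retention, both arms | 20:10 | 24:12 |
|---|---|---|
| 65% | 0.989 | 0.995 |
| 80% | 0.9995 | 0.9999 |
| 90% | >0.9999 | >0.9999 |

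In a deliberately extreme assumed case, 65% retained in STC and all 10 controls retained, P(X > 10) = 0.88.

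**4. Which Table 4 rules need the arm.**

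- Enrollment (30 accrued from at most 50 approached): pooled, no arm needed.
- Retention (at least 24/30): pooled, no arm needed.
- Completion (at least 14/20): STC arm only.
- Acceptability (at least 15/20): STC arm only.

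Two of four cannot be computed without identifying the STC women. Section 6.2 takes completion from the program evaluation, so answers about the video or workbook also mark individual women. This route does not depend on group size.

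**5. The statement on equal numbers.** Taken literally, equal arms after every six assignments means 3:3 per block, hence 15 v 15 at N = 30 and 18 v 18 at N = 36. That contradicts the 2:1 ratio in the same section and the 20–24 v 10–12 in Section 16.1.2. If it were true it would remove the size clue, but not the one in step 4.

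**The case against.** The strongest reply concerns scope. Section 19.0 masks outcome data analyses, and Section 16.1.2.3 uses outcome data to mean the preliminary efficacy measures. On that reading the STC-only rules were never meant to be masked. The plan also names a data analyst, a study biostatistician and a statistician, so an unmasked person could count those rules while the analyst stays masked. Both points stand as possible readings, although Section 16.1.1.1 does call feasibility and acceptability primary outcomes. Neither answers the size clue, which applies to any by-arm Aim 2 summary.

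The second reply is that little harm follows. Completion and acceptability are single-arm counts against thresholds set in advance, with no between-arm contrast to protect. Aim 2 rests mostly on fixed-score self-report instruments and is descriptive. Section 16.1.1.1 already counts partial use of the materials as completion, and thematic coding of open answers feeds no decision rule. The missing endorsement cut-off is a gap in definition that needs filling whether or not anyone is masked. All of this stands and sets the severity.

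A reader might go further and infer that the plan has no protection against bias at all. The documents do not support that. Two of the four rules use pooled counts, automated data collection does not depend on analyst masking, and nothing excludes withholding the arm variable during cleaning and scoring. A reader might also argue that re-scoring one woman could turn 14/20 into 13/20 and reverse a decision. That is true at the boundary of any threshold, masked or not, so it does not measure this problem.

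**Conclusion.** The point holds in a limited form. As described, analyst masking cannot be maintained once data are summarised by arm or the STC-only completion and acceptability rules are computed. Group size alone identifies STC with certainty as randomised, and with probability 0.989 to above 0.9999 after equal dropout in 20:10 arms at 65% to 90% retention. What masking can protect is work done without the arm variable, such as cleaning, scale scoring and reliability checks.

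This rests on three assumptions: blocks of six hold 4 STC and 2 control, dropout is independent between women, and masking means coded arm labels, which the plan does not specify. The survey forms are only listed as appendices, so how far the program evaluation differs by arm cannot be checked. Severity is low: no Table 4 figure, sample size or estimate changes, and no bias is shown.

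**What to change.** 1. In Section 19.0, limit the masking statement to steps done without the arm variable (cleaning, scale scoring, reliability checks), and say how it is done and by whom. State that Aim 1 completion and acceptability, and all by-arm summaries, are not masked.
2. For Aim 2, keep program-evaluation data in a separate file. Write and freeze the scoring and analysis code, including the cut for the sexual-concerns strata and the effect-size definition, on a file whose arm labels are randomly permuted in the same split (20:10 at N = 30). Then attach the true arm once. This works under 2:1 because the larger group in the permuted file is a random set of women and its results say nothing about STC.
3. Define the cut-off for endorsing an acceptability item before any T2 data are opened.
4. Reconcile the statement in Section 7.0 on equal arm numbers after every six assignments with the 2:1 ratio.

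The cost is some wording, one extra programming step, and a narrower masking claim. Sample size, visits and patient burden are unchanged.

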20.0 Participant Informed Consent

See separate Informed Consent document

22.0 Appendices

- Surveys or Data Collection Tools
 - Self-Report Materials
 - Medical Records Data Collection Form
- Recruitment Materials
 - Recruitment letter/email
 - Recruitment script
 - Recruitment flyer/brochure
